#### **6.5 Permitted Concomitant Medications and Procedures**

The following medications and procedures are permitted during the study:

- Antiemetics, including 5-HT3 serotonin receptor antagonists, may be used at the discretion of the investigator.
- Loperamide or other antidiarrheal should be used for symptomatic diarrhea at discretion of the investigator. The dose and regimen will be according to institutional guidelines. IVF should be given to prevent volume depletion.
- Growth factors (eg, granulocyte colony stimulating factor [G-CSF], granulocyte macrophage-colony stimulating factor [GM-CSF], recombinant erythropoietin) are permitted. Their use should follow published guidelines and/or institutional practice; however, alternative usage may be reviewed with the Janssen Clinical

or Medical Representative. Erythropoietin will be allowed in this study. Their use should follow published guidelines and/or institutional practice.

- Patients should be transfused with red cells and platelets as clinically indicated and according to institutional guidelines.
- Concomitant treatment with bisphosphonates will be permitted, as appropriate.
- Patients who experience worsening neuropathy from baseline may be observed for recovery and have dose reductions/delays as indicated in the protocol, and any supportive therapy or intervention may be initiated as appropriate at the discretion of the investigator.
- Supportive measures consistent with optimal patient care may be given throughout the study.

## **6.6 Precautions and Restrictions**

- Fluid deficit should be corrected before initiation of treatment and during treatment.
- Nonsteroidal anti-inflammatory drugs (NSAIDs) should be avoided with impaired renal function given reported NSAID-induced renal failure in patients with decreased renal function.

### **Pregnancy**

Pomalidomide can cause fetal harm when administered to a pregnant female. Pomalidomide is contraindicated in females who are pregnant. Pomalidomide is a thalidomide analogue and is teratogenic in both rats and rabbits when administered during the period of organogenesis. If this drug is used during pregnancy or if the patient becomes pregnant while taking this drug, the patient should be apprised of the potential risk to a fetus.

### **Embryo-Fetal Toxicity**

Pomalidomide is a thalidomide analogue and is contraindicated for use during pregnancy. Thalidomide is a known human teratogen that causes severe birth defects or embryo-fetal death. pomalidomide is only available through the pomalidomide REMS program.

Females of Reproductive Potential Females of reproductive potential must avoid pregnancy for at least 4 weeks before beginning pomalidomide therapy, during therapy, during dose interruptions and for at least 4 weeks after completing therapy.

Females must commit either to abstain continuously from heterosexual sexual intercourse or to use 2 methods of reliable birth control, beginning 4 weeks prior to initiating treatment with pomalidomide, during therapy, during dose interruptions, and continuing for 4 weeks following discontinuation of pomalidomide therapy. Two negative pregnancy tests must be obtained prior to initiating therapy. The first test should be performed within 10-14 days and

the second test within 24 hours prior to prescribing pomalidomide therapy and then weekly during the first month, then monthly thereafter in females with regular menstrual cycles, or every 2 weeks in females with irregular menstrual cycles.

#### Males

Pomalidomide is present in the semen of patients receiving the drug. Therefore, males must always use a latex or synthetic condom during any sexual contact with females of reproductive potential while taking pomalidomide and for up to 4 weeks after discontinuing pomalidomide, even if they have undergone a successful vasectomy. Male patients taking pomalidomide must not donate sperm.

#### Pregnancy Testing

Pomalidomide can cause fetal harm when administered during pregnancy.

Verify the pregnancy status of females of reproductive potential prior to initiating pomalidomide therapy and during therapy. Advise females of reproductive potential that they must avoid pregnancy 4 weeks before therapy, while taking pomalidomide, during dose interruptions and for at least 4 weeks after completing therapy.

Females of reproductive potential must have 2 negative pregnancy tests before initiating pomalidomide. The first test should be performed within 10-14 days, and the second test within 24 hours prior to prescribing pomalidomide. Once treatment has started and during dose interruptions, pregnancy testing for females of reproductive potential should occur weekly during the first 4 weeks of use, then pregnancy testing should be repeated every 4 weeks in females with regular menstrual cycles. If menstrual cycles are irregular, the pregnancy testing should occur every 2 weeks. Pregnancy testing and counseling should be performed if a patient misses her period or if there is any abnormality in her menstrual bleeding. Pomalidomide treatment must be discontinued during this evaluation.

#### Contraception

##### Females

Females of reproductive potential must commit either to abstain continuously from heterosexual sexual intercourse or to use 2 methods of reliable birth control simultaneously: one highly effective form of contraception – tubal ligation, IUD, hormonal (birth control pills, injections, hormonal patches, vaginal rings, or implants), or partner's vasectomy, and 1 additional effective contraceptive method – male latex or synthetic condom, diaphragm, or cervical cap. Contraception must begin 4 weeks prior to initiating treatment on study, during therapy, during dose interruptions, and continuing for 4 weeks following discontinuation of pomalidomide and 12 weeks following discontinuation of daratumumab. Reliable contraception is indicated even where there has been a history of infertility, unless due to hysterectomy. Females of reproductive potential should be referred to a qualified provider of contraceptive methods, if needed.

## 6.7 Management of Clinical Events

### Management of Hepatitis B Virus Reactivation

Primary antiviral prophylaxis is permitted as per local standard of care. Per protocol, HBV DNA testing by PCR is mandatory for subjects at risk for HBV reactivation.

For subjects who are diagnosed with HBV reactivation while on treatment, study treatment should be interrupted until the infection is adequately controlled. If the benefits outweigh the risks, study treatment may be resumed with concomitant antiviral prophylaxis as per local standard of care. Consult a liver disease specialist as clinically indicated.

Adverse drug reactions such as thrombocytopenia, diarrhea, fatigue, nausea, vomiting, and rash have been associated with pomalidomide treatment. Management guidelines regarding these events are outlined below. Further details of management of AEs are described in the pomalidomide IB.

### Prophylaxis Against Risk of Reactivation of Herpes Infection

Patients may be at an increased risk of infection including reactivation of herpes zoster and herpes simplex viruses. Antiviral therapy such as acyclovir, valacyclovir, or other antivirals may be initiated as clinically indicated. Other antivirals are also acceptable.

### Venous and Arterial Thromboembolism

Venous thromboembolic events (deep venous thrombosis and pulmonary embolism) and arterial thromboembolic events (myocardial infarction and stroke) have been observed in patients treated with pomalidomide. In Trial 2, where anticoagulant therapies were mandated, thromboembolic events occurred in 8.0% of patients treated with pomalidomide and low dose-dexamethasone (low-dose dex), and 3.3% of patients treated with high-dose dexamethasone. Venous thromboembolic events (VTE) occurred in 4.7% of patients treated with pomalidomide and Low-dose Dex, and 1.3% of patients treated with high-dose dexamethasone.

Arterial thromboembolic events include terms for arterial thromboembolic events, ischemic cerebrovascular conditions, and ischemic heart disease. Arterial thromboembolic events occurred in 3.0% of patients treated with pomalidomide and low-dose dex, and 1.3% of patients treated with high-dose dexamethasone.

Patients with known risk factors, including prior thrombosis, may be at greater risk, and actions should be taken to try to minimize all modifiable factors (e.g., hyperlipidemia, hypertension, smoking). Thromboprophylaxis is recommended, and the choice of regimen should be based on assessment of the patient's underlying risk factors.

### Prophylaxis Against Risk of Peptic Ulcer Disease

Patients may be at an increased risk of peptic ulcer disease while on corticosteroids with dexamethasone. Pantoprazole or other oral proton-pump inhibitor to prevent peptic disease for the duration of treatment with dexamethasone

### Nausea and/or Vomiting

Standard anti-emetics including 5-hydroxytryptamine 3 serotonin receptor antagonists are recommended for emesis if it occurs once treatment is initiated; prophylactic anti-emetics may also be considered at the physician's discretion. Dexamethasone should not be administered as an anti-emetic. Fluid deficit should be corrected before initiation of study drug and during treatment.

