#### Cycles 9-30 Maintenance (28-day cycle)

- Daratumumab 1800 mg SC q4wks on Day 1
- Pomalidomide 4 mg PO on Days 1-21 of 28-day cycle
- Dexamethasone 20 mg PO will be administered as a premedication prior to daratumumab injection on day 1 of daratumumab.
- Dexamethasone 20 mg PO weekly on non-daratumumab treatment days

During the study, assessments will be performed as shown in the Study Calendar and as clinically indicated.

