## 5.2 Exclusion Criteria

Patients meeting any of the following exclusion criteria are not to be enrolled in the study:

1. Prior exposure to non-daratumumab anti-CD38 monoclonal antibodies. Prior pomalidomide exposure in 1 or more previous lines of therapy allowed if partial remission (PR) or better achieved. No disease progression may have occurred within 60 days of receiving pomalidomide.
2. Clinically significant cardiac disease defined by any of the following criteria:
  1. New York Heart Association (NYHA) Class III or IV heart failure
  2. Unstable cardiac arrhythmia
  3. Unstable angina
  4. Myocardial infarction within the past 6 months.
3. Baseline prolongation of the QT interval (men  $> 450$  ms; women  $> 470$  ms), on concurrent drugs known to prolong the QT interval (see Appendix 12.3), or with ongoing proarrhythmic conditions.
4. Severe obstructive airway disease defined by forced expiratory volume at one second (FEV1)  $< 50\%$ .
5. Planned high-dose chemotherapy and autologous stem cell transplantation within 6, 28-day treatment cycles after starting on treatment.
6. Female patients who are lactating or have a positive serum pregnancy test during the screening period.
7. Failure to have fully recovered (ie,  $\leq$  Grade 1 toxicity) from the reversible effects of prior chemotherapy.
8. Major surgery within 14 days before enrollment.
9. Radiotherapy within 14 days before enrollment. If the involved field is small, 7 days will be considered a sufficient interval between treatment and study drug administration.
10. Infection requiring systemic intravenous antibiotic therapy or other serious infection within 14 days before study enrollment.
11. Systemic treatment, within 14 days before the first dose, with strong CYP3A inducers (rifampin, rifapentine, rifabutin, carbamazepine, phenytoin, phenobarbital, see Appendix 12.4), or use of Ginkgo biloba or St. John's wort.
12. Ongoing or active systemic infection including
  - Seropositive for human immunodeficiency virus (HIV)

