#### **6.4 Excluded Concomitant Medications and Procedures**

The following medications and procedures are prohibited during the study.

Systemic treatment with concurrent drugs known to prolong the QT interval (see Appendix 12.3)

Systemic treatment with any of the following metabolizing enzyme inducers should be avoided, unless there is no appropriate alternative medication for the patient's use:

- Strong CYP3A inducers: rifampin, rifapentine, rifabutin, carbamazepine, phenytoin, and phenobarbital. For a more comprehensive list of CYP3A inducers, please refer to Appendix 12.4.

The following medicinal products and procedures are prohibited during the study.

- Excluded foods and dietary supplements include St. John's wort and Ginkgo biloba.
- Any antineoplastic treatment with activity against MM, other than study drugs
- Radiation therapy (note that, in general, the requirement for local radiation therapy indicates disease progression)
- Platelet transfusions to help patients meet eligibility criteria are not allowed within 3 days prior to study drug dosing for any dosing day

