### 12.3 List of common QT prolonging drugs

Zofran  
Erythromycin  
Quinolones  
Azoles  
Sotalol  
Amiodarone  
Amitriptyline  
Fluoxetine  
Sertraline  
Venlafaxine  
Quetiapine  
Methadone  
Sumatriptan

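### The emesis guidance (6.5 and 6.7) permits and recommends 5-HT3 antagonists as a class, although 6.4 and Appendix 12.3 bar one of them, Zofran, as a QT-prolonging drug

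*Combined protocol and SAP*

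**What the plan says.** Section 6.4 begins with "The following medications and procedures are prohibited during the study". Its first item is "Systemic treatment with concurrent drugs known to prolong the QT interval (see Appendix 12.3". The next item concerns metabolizing enzyme inducers, which "should be avoided, unless there is no appropriate alternative medication". That softer wording belongs to the inducers; the QT item carries no exception.

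Appendix 12.3 is headed "List of common QT prolonging drugs". It has 13 entries, and the first is Zofran. Exclusion criterion 3 in section 5.2 uses the same appendix at entry, ruling out patients who are "on concurrent drugs known to prolong the QT interval (see Appendix 12.3), or with ongoing proarrhythmic conditions".

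Two later places deal with anti-emetics:

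- Section 6.5 permits them and names a class: "serotonin receptor antagonists, may be used at the discretion of the investigator".
- Section 6.7, under nausea and vomiting, recommends that class: "Standard anti-emetics including 5-hydroxytryptamine 3 serotonin receptor antagonists are recommended for emesis if it occurs once treatment is initiated". It also allows prophylactic anti-emetics at the physician's discretion, and it names one drug that is not to be used for this purpose, dexamethasone.

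**The concern.** The plan treats QT prolongation as a patient-safety matter both at entry and on study, but it does not carry the rule into the sections a clinician would consult when a patient vomits. Those sections endorse a whole drug class, one member of which is on the prohibited list. Because the 6.7 paragraph does name one excluded drug, a reader may well take it that there are no others.

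The guidance is likely to be used. Section 6.7 lists nausea and vomiting among the reactions associated with pomalidomide. Section 1.3.2.2 reports nausea in 31% of 103 patients given daratumumab with pomalidomide and dexamethasone. Section 6.3.2 lets daratumumab continue through Grade 3 nausea or vomiting that responds to anti-emetics.

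At stake are a patient's exposure to a drug the plan means to keep from them, and a protocol deviation by a clinician who followed the plan's own advice.

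**Working it through.** No arithmetic applies beyond counting, and the plan states no figure to reproduce. The check sets the relevant texts side by side.

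| Place | What it does | Refers to 6.4 or Appendix 12.3? |
|---|---|---|
| 5.2, exclusion 3 | Excludes patients taking QT-prolonging drugs at entry | Yes, Appendix 12.3 |
| 6.4 | Prohibits QT-prolonging drugs on study, no exception | Yes, Appendix 12.3 |
| 6.5 | Permits 5-HT3 antagonists as a class | No |
| 6.7, nausea and vomiting | Recommends 5-HT3 antagonists as a class | No |

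1. **Is the ban absolute?** Yes, as written. The clause about having no suitable alternative is attached to the enzyme inducers and does not reach the QT item.
2. **Does the class include a barred drug?** Yes. Zofran is ondansetron, a 5-HT3 antagonist, so 1 of the 13 entries falls in the permitted and recommended class. The drug's identity is the one step the document does not supply.
3. **Is there a carve-out?** No. The body cites Appendix 12.3 in two sections (5.2 and 6.4). Of the two sections giving 5-HT3 guidance, 0 of 2 cite it or 6.4. Nothing says which section prevails.
4. **Can the sections be reconciled?** Yes, by choosing a 5-HT3 antagonist that 6.4 does not bar. The emesis guidance does not tell the reader to do this. Absence from the appendix does not settle the choice, since its heading presents a list of common drugs and nothing says it is complete. The document does not say whether any other 5-HT3 antagonist prolongs the QT interval.
5. **Would the plan's monitoring pick up a use?** Not by schedule. The Schedule of Study Procedures marks ECG at screening only. Section 8.1.5 lists ECG parameters among the safety data but sets no time for them. An unscheduled ECG remains possible, since section 4.1 says "assessments will be performed as shown in the Study Calendar and as clinically indicated", and section 7.2 is to the same effect. Nothing in 6.5 or 6.7 prompts one.

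**The case against.** The strongest reply is that there is no true contradiction. A general permission for a class does not lift a specific ban on one member. Neither 6.5 nor 6.7 names ondansetron or sets 6.4 aside, and 6.4 stands immediately before 6.5. Investigators must consult Appendix 12.3 for every patient at eligibility, so they will have seen Zofran at its head. On this view the defect is a missing cross-reference. The ECG argument is a separate monitoring question, and it rests on a calendar read from PDF in which at least one other row, chest x-ray, has no mark at all.

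Much of this stands. The sections can be followed together, the ban is findable, and the effect on patients cannot be quantified. The ECG point bears on how a lapse would be noticed and is not evidence that the emesis text is wrong; it assumes the calendar row was read completely. The remark about the appendix not being exhaustive would matter in practice only if an unlisted member of the class also prolongs the QT interval, which the document does not address.

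What does not stand is that the gap is therefore only editorial. The permitted list and the recommendation, read as written, cover a drug that the plan prohibits, and treating staff are left to infer a safety restriction that could be stated in one phrase.

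**Conclusion.** The concern holds. Sections 6.5 and 6.7 endorse 5-HT3 antagonists without excepting those that 6.4 prohibits, and Zofran is one of them. In the text, the omission affects both sections that give 5-HT3 guidance. Its extent in patients is unknown, because the document gives no rate of ondansetron or other 5-HT3 antagonist use; the 31% nausea figure shows only that the guidance is likely to matter.

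The conclusion rests on the identity of Zofran as a 5-HT3 antagonist and on reading the 6.4 exception as confined to enzyme inducers. The remark on scheduled ECGs also assumes that the calendar row is complete. This is a matter of safety and conduct that should be corrected. The primary endpoint, the sample size of 40 and the analysis are unaffected.

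**What to change.** In 6.5 and in the nausea and vomiting paragraph of 6.7, add after the mention of 5-HT3 antagonists: except drugs prohibited under Section 6.4 (known to prolong the QT interval, including those in Appendix 12.3). This costs one phrase in two sections and is sufficient on its own.

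If ondansetron is meant to be available, the alternative is to state that exception in 6.4 together with ECG checks, and to add a sentence on whether exclusion criterion 3 still applies to a patient taking it at entry. That route adds procedures. Neither route changes the design, sample size or analysis.

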## Diarrhea

Prophylactic antidiarrheals will not be used in this protocol. However, diarrhea should be managed according to clinical practice, including the administration of antidiarrheals once infectious causes are excluded. Fluid intake should be maintained to avoid dehydration. Fluid deficit should be corrected before initiation of treatment and during treatment.

## Hepatotoxicity

Hepatic failure, including fatal cases, has occurred in patients treated with pomalidomide. Elevated levels of alanine aminotransferase and bilirubin have also been observed in patients treated with pomalidomide. Monitor liver function tests monthly. Stop pomalidomide upon elevation of liver enzymes and evaluate. After return to baseline values, treatment at a lower dose may be considered.

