### **6.3 Dose-Modification Guidelines**

No daratumumab dose modification (increase or decrease) is permitted during the study. Guidelines for pomalidomide and dexamethasone dose modifications are provided in Sections 6.3.3 and 6.3.4, respectively, although are only guidelines and not intended to supersede the clinical judgment of the treating physician.

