#### **6.3.1 Criteria for Beginning or Delaying a Subsequent Treatment Cycle**

Treatment with Daratumumab, Pomalidomide, and Dexamethasone will use a cycle length of 28 days. For a new cycle of treatment to begin, the patient must meet the following criteria:

- ANC must be  $\geq 1,000/\text{mm}^3$ .
- Platelet count must be  $\geq 75,000/\text{mm}^3$
- All other nonhematologic toxicity must have resolved to  $\leq$  Grade 2 or to the patient's baseline condition for cardiac toxicities (See Table 6.4 for definition of cardiac toxicities).

If the patient fails to meet the above-cited criteria for initiation of the next cycle of treatment, dosing should be delayed for 1 week. At the end of that time, the patient should be re-evaluated to determine whether the criteria have been met. If the patient continues to fail to meet the above-cited criteria, delay therapy and continue to reevaluate. The maximum delay before treatment should be discontinued will be 4 weeks or at the discretion of the Principal Investigator.

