other non-hematologic toxicity (non cardiac) <math>\geq</math> Grade 3	
 
Hold (interrupt) pomalidomide. Follow at least weekly.
 
If resolves to <math>\leq</math> grade 2 prior to Day 21, restart at next lower dose level and continue through Day 21.
 
	
 
Omit pomalidomide for remainder of cycle.
 
See Instructions for Initiation of a New Cycle (6.3.1) and reduce the dose by 1 dose level.
 

Grade 3 dyspnea, cardiac edema, arrhythmias OR any increase in NYHA class or NTproBNP <math>\geq</math> 30%  Grade 4	
 
Hold Pom. Follow biweekly. If resolves to baseline prior to Day 21, restart at next lower dose and continue through Day 21. If does not resolve to baseline by day 21, hold Pom for remainder of cycle. CC-4047 at next lower dose level and continue through Day 21.
 
Discontinue pomalidomide.
 
	
 
Omit pomalidomide for remainder of cycle.
 
See Instructions for Initiation of a New Cycle (6.3.1) and reduce the dose by 1 dose level.
 
Discontinue pomalidomide.
 

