#### Dosage Adjustment for Patients with Hepatic Impairment

For patients with mild or moderate hepatic impairment (Child-Pugh classes A or B), the recommended starting dose is 3 mg daily (25% dose reduction). For patients with severe hepatic impairment (Child-Pugh class C), the recommended dose is 2 mg (50% dose reduction)

Permanently discontinue pomalidomide for angioedema, skin exfoliation, bullae, or any other severe dermatologic reaction.

For other Grade 3 or 4 toxicities, hold treatment and restart treatment at 1 mg less than previous dose when toxicity has resolved to  $\leq$  to Grade 2 at the physician's discretion.

If pomalidomide is discontinued for toxicity, the patient may continue on study receiving daratumumab per study schedule with dexamethasone alone without pomalidomide.

Once pomalidomide is reduced for any toxicity, the dose may not be re-escalated.

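### After a Grade 3 or higher liver-enzyme rise, section 6.7 requires return to baseline before pomalidomide is reconsidered, Table 6-3 restarts it at Grade 2 or less, and the protocol does not say which prevails

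*Combined protocol and SAP*

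**What the plan says.** Section 6.7, Hepatotoxicity, notes that hepatic failure, including fatal cases, has occurred with pomalidomide. It asks for monthly liver tests and then gives the rule: "Stop pomalidomide upon elevation of liver enzymes and evaluate. After return to baseline values, treatment at a lower dose may be considered".

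Section 6.3 handles the same event through general rules:

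- **Table 6-3.** The row whose label begins "other non-hematologic toxicity (non cardiac" covers Grade 3 or higher. For onset on days 2-14 the drug is held and, if the toxicity comes down to no more than "grade 2 prior to Day 21, restart at next lower dose level and continue through Day 21". For onset on day 15 or later the drug is omitted for the rest of the cycle, the reader is sent to section 6.3.1, and the dose drops one level.
- **Section 6.3.1.** For a new cycle to begin: "All other nonhematologic toxicity must have resolved to" Grade 2 or less. Baseline is named only for cardiac toxicities.
- **Section 6.3.3, closing text.** "For other Grade 3 or 4 toxicities, hold treatment and restart treatment at 1 mg less than previous dose when toxicity has resolved to" Grade 2 or less, at the physician's discretion. It adds: "Once pomalidomide is reduced for any toxicity, the dose may not be re-escalated".
- **Section 6.3, opening.** The pomalidomide and dexamethasone guidance is "only guidelines and not intended to supersede the clinical judgment of the treating physician".

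**The concern.** Two parts of one protocol set different recovery levels for restarting the same drug after the same event. Baseline is stricter than Grade 2 for any patient whose starting value was lower than Grade 2. Neither the liver paragraph nor Table 6-3 refers to the other.

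The stake is patient safety. The stricter rule sits beside the protocol's own statement that fatal hepatic failure has occurred with this drug. A physician who adjusts doses from the table, which is where dose changes are normally looked up, could resume pomalidomide before the condition in section 6.7 is met.

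A smaller gap lies below Grade 3. There the table's residual row does not apply, and section 6.7 stops the drug with no grade, multiple of the upper limit of normal (ULN) or stated reference point.

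**Working it through.** No figure in the plan bears on this point, so the check sets the rules side by side.

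| Rule | Applies to | Recovery needed | Dose on resumption | Force |
|---|---|---|---|---|
| 6.7 Hepatotoxicity | liver-enzyme elevation, no threshold | return to baseline | lower dose | may be considered |
| Table 6-3 residual row, onset days 2-14 | Grade 3 or higher | Grade 2 or less before day 21 | one level lower, same cycle | instruction within guidelines |
| Table 6-3 residual row, onset day 15 or later | Grade 3 or higher | as 6.3.1: Grade 2 or less | one level lower | 6.3.1 is a minimum gate |
| 6.3.3 closing text | other Grade 3 or 4 toxicities | Grade 2 or less | 1 mg less | physician's discretion |

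**Step 1: do the rules agree on dose?** Yes. Table 6-2 steps through 4, 3, 2 and 1 mg, so one level is 1 mg. From the starting dose, every section 6.3 route gives 4 - 1 = 3 mg, and section 6.7 also requires a lower dose. The disagreement is only about when the drug may resume.

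**Step 2: is there a patient for whom the rules give different answers?** Yes. Suppose enzymes were normal at entry, reach Grade 3 on cycle 1 day 8 and are Grade 2 on day 15. Chemistry is scheduled on both days. Table 6-3 restarts pomalidomide at 3 mg through day 21, which is up to 21 - 15 + 1 = 7 daily doses. Section 6.7 does not yet allow the drug to be reconsidered. This is an illustration, not an estimate of frequency.

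**Step 3: what about later onset?** If the Grade 3 value first appears on day 15 or later, the table omits the drug for that cycle and refers to 6.3.1. Grade 2 meets that gate, so the next cycle may begin. The gate does not itself tell anyone to restart pomalidomide, and a physician can pass it and still wait for baseline. The explicit same-cycle restart instruction is therefore confined to onset on days 2-14.

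**Step 4: does any text rank the rules?** None does. Section 6.3 defers to clinical judgment without mentioning section 6.7, and section 6.7 describes its own content as management guidelines. The drafting elsewhere does not settle it either:

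- Where Table 6-3 wants recovery stricter than Grade 2, it says so: Grade 1 or less for non-blistering rash, Grade 1 or less or baseline for neuropathy, baseline for cardiac events. It has no such entry for liver enzymes.
- The section 6.7 rule on severe skin reactions is repeated in section 6.3.3. The liver rule is not.
- The thrombocytopenia and neutropenia paragraphs of section 6.7 point to the dose-modification recommendations. The liver paragraph does not.

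**Step 5: the trigger below Grade 3.** Section 5.1 admits AST up to 2.0 x ULN and ALT below 3.0 x ULN, so some patients may enter with raised values. The stop sentence does not say whether elevation is judged against normal or against the patient's own baseline.

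**The case against.** The strongest reply is that the protocol can be read without contradiction. Section 6.7 is specific to the liver and the Table 6-3 row is residual, so the specific rule should govern. Section 6.3 leaves its guidance subject to clinical judgment, and the Grade 2 restart in section 6.3.3 is discretionary. A physician who waits for baseline breaches nothing.

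That reading is reasonable, and much of it stands. But it permits the stricter course without requiring it, and the protocol does not state the precedence on which it depends.

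Three stronger readings might be inferred, and the documents do not support them:

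- *That the protocol compels a restart above baseline.* It does not, for the reasons just given.
- *That the rules collide at every scheduled chemistry draw.* Section 6.3.1 governs subsequent cycles, so cycle 1 day 1 is outside it. Its Grade 2 criterion is a necessary condition, compatible with waiting for baseline. A count of draws would not measure harm.
- *That there is also a conflict below Grade 3.* The table's residual row is silent there and section 6.7 stands alone. Its resumption test suggests that elevation is meant relative to baseline, and section 6.7 refers to the pomalidomide Investigator's Brochure for further detail, which is not available here. What is missing is detail.

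Twice-yearly committee review and chemistry at least once per cycle help detect liver events. They do not tell the treating physician which restart rule to use.

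**Conclusion.** The inconsistency is real but limited. For a Grade 3 or higher liver-enzyme rise that has improved to Grade 2 or less but not to baseline, section 6.7 withholds pomalidomide. The Table 6-3 residual row restarts it for onset on days 2-14, section 6.3.3 permits the restart, and section 6.3.1 does not prevent it at the next cycle. No text says that section 6.7 prevails.

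This rests on two readings: that liver-enzyme rises fall in the residual row, since the table has no liver row, and that baseline means the patient's own pre-treatment value.

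The number of patients affected cannot be estimated from the documents. No effect on the primary analysis is claimed. The correction should be made because following the table as written can restart the drug above the level set by the protocol's own liver rule, and the remedy is only wording. The undefined trigger below Grade 3 is a secondary clarification.

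**What to change.** 1. In the Table 6-3 residual row, and in the section 6.3.3 sentence on other Grade 3 or 4 toxicities, add: *except liver-enzyme elevation, see section 6.7: restart one dose level lower only after return to baseline.*
2. State that this exception applies to pomalidomide only. Leave the section 6.3.1 gate unchanged, and leave daratumumab resuming at Grade 2 or less under section 6.3.2. The protocol already separates the drugs in a related case: "If pomalidomide is discontinued for toxicity, the patient may continue on study receiving daratumumab per study schedule with dexamethasone alone without pomalidomide".
3. As a secondary clarification, state in section 6.7 the grade or ULN multiple, relative to the patient's baseline, that triggers the stop. It should not default to any rise above baseline. A trivial fluctuation would then force a hold and, on resumption, a reduction that section 6.3.3 does not allow to be reversed. Nor should bilirubin be added to the stop rule by default, since that sentence names only liver enzymes.

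The cost is an amendment of wording: two exception phrases, one scope statement and one trigger definition. No new tests or visits are needed, because AST and ALT are already in the chemistry panel. The downside is that some patients may spend longer off pomalidomide; the documents do not allow that number to be estimated.
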